### 3.2.8.PD-L1

Table 26: PD-L1 High status

	(N=)
PD-L1 High status	
Missing data	
Low/Negative	
High	

### 3.3. TREATMENT

#### 3.3.1. DURVALUMAB TREATMENT

Table 27: Durvalumab compliance

	(N=)
1 dosis of Durvalumab	
No	
Yes	
2 dosis of Durvalumab	
No	
Yes	
3 dosis of Durvalumab	
No	
Yes	
Number of Durvalumab dosis	
N	
Mean (95%CI)	
SD	
Median (95%CI)	
Range	
Number of Durvalumab dosis	
1 dosis	
2 dosis	
3 dosis	

Table 28: Durvalumab dosage

	(N=)
Dosis of Durvalumab week 1	
1500	
Dosis of Durvalumab week 5	
1500	
Dosis of Durvalumab week 9	
1500	
None	

Table 29: Durvalumab Not administered reasons

	(N=)
Not administered reasons week 1	

	(N=)
Not administered reasons week 5	
Not administered reasons week 9	

Table 30: Durvalumab delay

	(N=)
Patients with at least one delay of Durvalumab	
No	
Yes	
Number of doses of Durvalumab delayed	
None	
1 delay	
2 delays	
3 delays	
Dose of Durvalumab delayed	
N	
Mean (95%CI)	
SD	
Median (95%CI)	
Range	
Durvalumab dose delay week 1	
Yes	
No	
Durvalumab dose delay week 5	
Yes	
No	
Durvalumab dose delay week 9	
Yes	
No	
Reason Durvalumab dose delay week 1	
Reason Durvalumab dose delay week 5	
Reason Durvalumab dose delay week 9	

### 3.3.2. TREMELIMUMAB TREATMENT

Table 31: Tremelimumab compliance

	(N=)
1 dosis of Tremelimumab	
Yes	
2 dosis of Tremelimumab	
Yes	
3 dosis of Tremelimumab	
No	
Yes	
Number of Tremelimumab dosis	
N	
Mean (95%CI)	
SD	
Median (95%CI)	
Range	
Number of Tremelimumab dosis	
1 dosis	
2 dosis	
3 dosis	

Table 32: Tremelimumab dosage

	(N=)
Dosis of Tremelimumab week 1	
75	
Dosis of Tremelimumab week 5	
75	
Dosis of Tremelimumab week 9	
75	

Table 33: Tremelimumab Not administered reasons

	(N=)
Not administered reasons week 1	
Not administered reasons week 5	
Not administered reasons week 9	

Table 34: Tremelimumab delay

	(N=)
Patients with at least one delay of Tremelimumab	
No	
Yes	
Number of doses of Tremelimumab delayed	
None	
1 delay	
2 delays	
3 delays	
Dosis of Tremelimumab delayed	
N	
Mean (95%CI)	
SD	
Median (95%CI)	
Range	
Tremelimumab dosis delay week 1	
Yes	
No	
Tremelimumab dosis delay week 5	
Yes	
No	
Tremelimumab dosis delay week 9	
Yes	
No	
Reason Tremelimumab dosis delay week 1	
Reason Tremelimumab dosis delay week 5	
Reason Tremelimumab dosis delay week 9	

Table 35: List of patients with Durvalumab or Tremelimumab delay

Patient ID	Reason Durvalumab delay in week 5	Reason Tremelimumab delay in week 5

### 3.3.3. RADIOTHERAPY TREATMENT

Table 36: Radiotherapy treatment details

	(N=)
Radiotherapy Sessions (total number)	
N	
Mean (95%CI)	
SD	
Median (95%CI)	
Range	
Radiotherapy Sessions (total number)	
10	
25	
27	
28	
30	
31	
32	
33	
35	
66	
Radiotherapy Fractions (per week)	
N	
Mean (95%CI)	
SD	
Median (95%CI)	
Range	
Radiotherapy Fractions (per week)	
Missing data	
4	
5	
10	
23	
Radiotherapy Dose per Fraction (Gy)	
N	
Mean (95%CI)	
SD	
Median (95%CI)	
Range	
Radiotherapy Dose per Fraction (Gy)	
Missing data	
2	
4	
Radiotherapy Doses Minor Pelvis (Gy)	
N	
Mean (95%CI)	
SD	
Median (95%CI)	
Range	
Radiotherapy Doses Minor Pelvis (Gy)	
Missing data	

	(N=)
46	
51	
52	
Radiotherapy Total Dose administered in bladder (Gy)	
N	
Mean (95%CI)	
SD	
Median (95%CI)	
Range	
Radiotherapy Total Dose administered in bladder (Gy)	
50	
54	
60	
61	
64	
65	
66	
Radiotherapy treatment duration (weeks)	
N	
Mean (95%CI)	
SD	
Median (95%CI)	
Range	

## Radiotherapy interruptions

Table 37: Radiotherapy interruptions

	(N=)
Radiotherapy Interruption	
Yes	
No	
Number of radiotherapy interruptions	
N	
Mean (SD)	
Median (Range)	
Number of radiotherapy interruptions	
1 interruption	
2 interruptions	
3 interruptions	
None	
Radiotherapy ReStart	
Yes	
No	
NA	
Total duration of radiotherapy interruptions (days)	
N	
Mean (SD)	
Median (Range)	
Radiotherapy Interruption Reason	

---

---

(N=)

---

### **List of patients with their radiotherapy interruptions details**

Table 38: List of patients with their radiotherapy interruptions details

Patient ID	Hospital	Number of radiotherapy interruptions	Radiotherapy restarted	Radiotherapy interruption total duration (days)	Reason for radiotherapy interruption

## 3.4. END OF TREATMENT

Table 39: End of treatment details

	(N=)
Treatment duration (weeks)	
N	
Mean (95%CI)	
SD	
Median (95%CI)	
Range	
End Treatment Reason	
Unacceptable toxicity	
AE not related to treatment	
Complete the protocol treatment	

**List of patients with their end of treatment reason and treatment duration:**

Table 40: End of treatment reason and treatment duration by patient

Patient ID	Hospital	Treatment duration (weeks)	End of treatment reason

## 3.5. MEDIAN FOLLOW-UP

Table 41: Median follow-up (overall)

	(N=)
Follow-up in months	
N	
Mean (95%CI)	
SD	
Median (95%CI)	
Range	

## 3.6. MEDIAN FOLLOW-UP (ONLY ALIVE PATIENTS)

Table 42: Median follow-up (only alive patients)

	(N=)
Follow-up in months	
N	
Mean (95%CI)	
SD	
Median (95%CI)	
Range	

Table 43: List of patients: follow-up (months)

Patient ID	Hospital	Status	Overall Survival Time (months)

### 3.7. RESPONSE EVALUATION TO THERAPY

Table 44: Response evaluation: Cystoscopy details

		(N=)
Time since end of treatment until Cystoscopy (weeks)		
N		
Mean (95%CI)		
SD		
Median (95%CI)		
Range		
Cystoscopy done		
Yes		
No		
Reason response evaluation not done		

#### List of patients without Cystoscopy

Table 45: List of patients without Cystoscopy

Patient ID	Hospital	Cystoscopy done	Reason Cystoscopy not done	Death Reason

### 3.8. PRIMARY EFFICACY ANALYSIS

Efficacy of durvalumab plus tremelimumab with concurrent radiotherapy in terms of pathological response rate (Response evaluation by cystoscopy 6 weeks after end of RT).

#### Muscle Invasive Bladder Cancer

Table 46: Response Evaluation: Muscle-invasive bladder cancer

Muscle-invasive bladder cancer	N	%	95%CI
Cystoscopy not done			
Yes			
No			
Total			

#### Non Invasive Bladder Cancer

Table 47: Response Evaluation: Non Invasive Bladder Cancer

Non Invasive Bladder Cancer	N	%	95%CI
Cystoscopy not done			
Yes			
No			
Total			

#### Non-Invasive bladder cancer (including Muscle invasive)

Table 48: Response Evaluation: Non Invasive Bladder Cancer (including Muscle Invasive)

Non Invasive Bladder Cancer	N	%	95%CI
Cystoscopy not done			
Yes (Non Invasive Bladder Cancer)			
Yes (Muscle Invasive Bladder Cancer)			
No			
Total			

Table 49: Response Evaluation: TNM

(N=)	
T Stage	
T0	
T1	
T2	
T4	
T Stage (including Not evaluated)	

	(N=)
Cytoscopy not done	
T0	
T1	
T2	
T4	
N Stage	
N0	
N Stage (including Not evaluated)	
Cytoscopy not done	
N0	
M Stage	
M0	
M Stage (including Not evaluated)	
Cytoscopy not done	
M0	

### 3.9. SECONDARY OBJECTIVE 1A: BLADDER PRESERVATION AT 6 WEEKS AFTER RT

**Bladder preservation. Rate of patients with bladder preserved (at 6 weeks after RT)**

Table 50: Response Evaluation: Post therapy radical surgery/salvage cystectomy required (aprox. 6 weeks after RT). Immediate salvage cystectomies

		(N=)
Radical Surgery. Immediate salvage cystectomies		
No		
Radical Surgery (including Not evaluated). Immediate salvage cystectomies		
Cytoscopy not done		
No		

#### Details of Response Evaluation

Table 51: List of patients with Response Evaluation Non-invasive Invasive Bladder or without Cystoscopy (6 weeks after end of RT)

Patient ID	Hospital	Muscle Invasive Bladder	Non Invasive Bladder Cancer	T Stage	N Stage	M Stage	Radical Surgery

### 3.10. SECONDARY OBJECTIVE 1B: BLADDER PRESERVATION IMMEDIATE AND LATE SALVAGE CYSTECTOMIES

**Bladder preservation: Rate of immediate and late salvage cystectomies.** “Post therapy radical/surgery cystectomy” is used to calculate the rate at 3, 6 and 9 months (assuming a margin of one week, 7 days).

- Immediate salvage cystectomies
- Late salvage cystectomies

Table 52: Late salvages cystectomies at 3 months

Late salvages cystectomies at 3 months (all patients)	N	%	95%CI
No (Follow-up>=3m)			
Death before 3m			
Total			

Table 53: Late salvages cystectomies at 6 months

Late salvages cystectomies at 6 months (all patients)	N	%	95%CI
No (Follow-up>=6m)			
Death before 6m			
Total			

Table 54: Late salvages cystectomies at 6 months (excluding patients with Follow-up less than 6 months)

Late salvages cystectomies at 6 months (excluding patients with Follow-up less than 6 months)	N	%	95%CI
No (Follow-up>=6m)			
Total			

Table 55: Late salvages cystectomies at 9 months

Late salvages cystectomies at 9 months (all patients)	N	%	95%CI
Yes			
No (Follow-up>=9m)			
Death before 9m			
Total			

Table 56: Late salvages cystectomies at 9 months (excluding patients with Follow-up less than 9 months)

Late salvages cystectomies at 9 months (excluding patients with Follow-up less than 9 months)	N	%	95%CI
Yes			
No (Follow-up>=9m)			
Total			

Table 57: Late salvages cystectomies at any time

Late salvages cystectomies at any time (all patients)	N	%	95%CI
Yes			
No			
Death			
Total			

Table 58: Late salvages cystectomies (any time) excluding deaths

Late salvages cystectomies at any time (excluding deaths)	N	%	95%CI
Yes			
No			
Total			

Table 59: List of patients with Late salvages cystectomies (any time)

Patient ID	Hospital	Late salvage cystectomy	Date Late salvage cystectomy	Time since start of treatment until late salvage cystectomy (months)

### 3.11. SECONDARY OBJECTIVE 1C: BLADDER PRESERVATION EFS

Event Free Survival (EFS) with bladder preserved free of tumor, defined as the time from the start of immunotherapy to either the date of cystectomy or the date of recurrence of muscle-invasive bladder carcinoma or metastasis.

#### EFS Bladder preservation

Table 60: Bladder preservation: Event Free Survival

EFS (event)	N	%	95%CI
Event/Death			
No			
Total			

Table 61: Type of event: EFS bladder preserved

Type of event: EFS bladder preserved	(N=)
No	
Late salvage cystectomy/Bladder relapse	
Bladder relapse/Metastases	
Bladder relapse	
Metastases	
Death	

Table 62: Survival Median/Mean EFS

	Median	95%CI	Mean	95%CI
EFS				

#### 3.11.1. EFS BLADDER PRESERVATION ESTIMATED AT 6, 12, 18 AND 24 MONTHS (KAPLAN-MEIER)

Table 63: EFS bladder preserved at 6, 12, 18 and 24 months

EFS bladder preserved	Events (%, total N)	Patients at risk	% estimated cumulative survival ratio	95% IC
At 6 months				
At 12 months				
At 18 months				

EFS bladder preserved	Events (% total N)	Patients at risk	% estimated cumulative survival ratio	95% IC
At 24 months				

Note: Estimated using Kaplan-Meier product-limit method

### 3.11.1.1. FIGURE: EFS BLADDER PRESERVATION

#### List of patients. Events: EFS bladder preserved

Table 64: List of patients with event for EFS bladder preserved

Patient ID	Hospital	Event EFS bladder preserved	Date EFS bladder preserved

### 3.12. SECONDARY OBJECTIVE 1D: EVENT FREE SURVIVAL (SPECIFIC)

Event Free Survival (EFS) specific:

- 1) M1 o N1 (metastases) is an event independently of presence of Salvage cystectomy
- 2) Local recurrence (bladder relapse) without Salvage cystectomy.

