### **2.2. Secondary objective(s)**

- To determine the rate of patients with bladder preserved, the rate of immediate and late salvage cystectomies and the survival with bladder preserved free of tumor, defined as the time from the start of immunotherapy to either the date of cystectomy or the date of recurrence of muscle- invasive bladder carcinoma or metastasis.
- To determine the disease-free survival, defined as the time from the start of therapy to the date of recurrence of muscle invasive bladder carcinoma or metastases, and overall survival, defined as the time from the start of immunotherapy to the date of death due to any cause
- To assess the safety profile and tolerability of the combination of durvalumab plus tremelimumab with concurrent radiotherapy
- To evaluate the long-term functionalism and late sequelae of the treatment in the preserved bladders

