## **3. STUDY DESIGN**

### **3.1. Overview of study design**

This is an open-label, multicenter, phase II trial of the combination of durvalumab plus tremelimumab with concurrent normofractionated radiotherapy in patients with localized muscle invasive bladder cancer treated with a selective multimodality bladder conservative approach. The study will be conducted in a small group of centers with multidisciplinary teams with wide experience in multimodality bladder preservation therapy (7 centers belonging to SOGUG).

The treatment consisted of initial transurethral resection (TUR) of the tumor, with multiple random biopsies of normal-appearing bladder urothelium, followed by durvalumab 1500 mg i.v. plus tremelimumab 75 mg i.v., every 4 weeks for a total of 3

doses. Two weeks after the initiation of immunotherapy, normofractionated external-beam radiotherapy with high-energy photons will be started. Radiotherapy will be administered concurrently with immunotherapy at doses of 46 Gy to the minor pelvis and 64-66 Gy to the bladder. Six weeks after the end of radiotherapy as an efficacy determination, ALL patients will undergo a new cystoscopy with biopsies of the tumor bed and all residual present lesions. Response is defined as an absence of invasive cancer at post immunotherapy biopsy ( $\leq$ cT1). Patients with response to immunotherapy will be candidates to bladder preservation, whereas in those with residual muscle invasive tumor the possibility of salvage radical cystectomy must be evaluated. Patients developing an isolated bladder invasive relapse during follow-up will be also possible candidates to salvage cystectomy, whereas those developing a superficial relapse in the preserved bladder will be managed with TUR and intravesical BCG.

To monitor accurately the potential toxicity of radiotherapy associated with durvalumab and tremelimumab, an initial cohort of 5 patients of first Simon Optimax stage of 12 patients, will be treated. If no dose limiting toxicity is observed in  $\geq$ 2 of these patients in the 12 weeks of observation period, the rest of patients will be treated at full doses. In contrast, if severe toxicity is observed in  $\geq$ 2 of these patients, 3 additional patients will be treated. If dose limiting toxicity is seen in one of these additional patients, the therapeutic regimen will be modified in the subsequent ones, administering full doses of durvalumab but discontinuing tremelimumab after the first dose.

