Patients will be followed up every 3 months the first year, every 4 months the second year and every 6 months thereafter with abdomen and pelvis CT scan, Rx thorax, urine cytology. Additional cystoscopy and bladder biopsy will be performed anytime in case of detection abnormalities in the cytology or imaging studies. The study will be closed 2 years after the last patient inclusion.

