### **4.1. Inclusion criteria**

For inclusion in the study, patients should fulfill the following criteria:

1. Patients diagnosed with urothelial carcinoma of the bladder, in clinical stages T2-4a N0 M0, who are not candidates for radical cystectomy by medical reasons, refusal or patient's choice.
2. Written informed consent obtained from the patient prior to performing any protocol-related procedures, including screening evaluations
3. Age >18 years at time of study entry or Adult male or female (according to age of majority as defined as ≥18 years)

4. Patients must have ECOG performance status 0 or 1.
5. A paraffin-embedded tumor sample must be available for the associate molecular study.
6. Body weight >30 Kg.
7. Adequate normal organ and marrow function as defined below:
  - Haemoglobin  $\geq 9$  g/dL
  - Absolute neutrophil count (ANC  $\geq 1.5$  (or 1.0)  $\times$  ( $> 1500$  per mm $^3$ )
  - Platelet count  $\geq 100$  (or 75)  $\times 10^9$ /L ( $>75,000$  per mm $^3$ )
  - Serum bilirubin  $\leq 1.5 \times$  institutional upper limit of normal (ULN). This will not apply to patients with confirmed Gilbert's syndrome (persistent or recurrent hyperbilirubinemia that is predominantly unconjugated in the absence of hemolysis or hepatic pathology), who will be allowed only in consultation with their physician.
  - AST (SGOT)/ALT (SGPT)  $\leq 2.5 \times$  institutional upper limit of normal unless liver metastases are present, in which case it must be  $\leq 5$  x ULN
  - Measured creatinine clearance (CL)  $>40$  mL/min or Calculated creatinine clearance CL  $>40$  mL/min by the Cockcroft-Gault formula (Cockcroft and Gault 1976) or by 24-hour urine collection for determination of creatinine clearance:

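### Read literally, SAP 3.12 EFS (specific) lets later surgery decide whether a bladder relapse counts, and no SAP section analyses the protocol's disease-free survival exactly

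*Combined protocol and SAP*

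**What the plan says.** SAP 3.12 defines EFS (specific), secondary objective 1d, by two items. The first is "M1 o N1 (metastases) is an event independently of presence of Salvage cystectomy". The second is "Local recurrence (bladder relapse) without Salvage cystectomy". Death appears in Tables 65 and 66 but not in the text. Kaplan-Meier estimates at 6, 12, 18 and 24 months follow in Table 68, and prognostic and Cox analyses in Tables 128 to 151.

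The protocol has no such endpoint; in its Table 8, label 1d is overall survival. Protocol 2.2 sets "disease-free survival, defined as the time from the start of therapy to the date of recurrence of muscle invasive bladder carcinoma or metastases" as a secondary outcome. Table 8 row 1c lists the same two events under a bladder-preservation label. Neither carries a condition on surgery.

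On the order of events, protocol 3.1 says "Patients developing an isolated bladder invasive relapse during follow-up will be also possible candidates to salvage cystectomy". Surgery therefore comes after the relapse.

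SAP 3.11 (objective 1c) runs from the start of immunotherapy "to either the date of cystectomy or the date of recurrence of muscle-invasive bladder carcinoma or metastasis". Its Table 61 has the event row "Late salvage cystectomy/Bladder relapse". Table 66, for EFS (specific), keeps the other rows of Table 61 and omits that one.

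**The concern.** The two items of SAP 3.12 are worded in contrast: surgery is irrelevant to metastasis but decisive for local relapse. Under that rule two patients with the same relapse on the same day are coded differently according to what happens afterwards. A relapse followed by cystectomy either disappears or moves to the date of a later metastasis or death. The curve would then partly measure how often relapses are operated on.

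Eligibility adds to this. Patients enter as "not candidates for radical cystectomy by medical reasons, refusal" or by their own choice, so the cohort mixes people who are unfit for surgery with people who decline it. Only an operable patient can have a relapse removed. The hazard ratios for age, ECOG and creatinine clearance in Table 149 could therefore partly reflect fitness for surgery.

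Two further terms are open. SAP 3.15 and 3.16 use bladder relapse for muscle-invasive and non-muscle-invasive events respectively, and 3.12 does not say which it means. Nor does its text say that death is an event.

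**Working it through.** The documents give no event rate, target or power for this endpoint, so there is no planned figure to reproduce. The first step is to compare the definitions.

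| Event | Protocol 2.2 DFS and Table 8 row 1c | SAP 3.11 | SAP 3.12, literal | SAP 3.13 PFS |
|---|---|---|---|---|
| Muscle-invasive relapse, not operated | yes | yes | yes | yes |
| Muscle-invasive relapse, cystectomy follows | yes | yes | **no** | yes |
| Metastasis | yes | yes | yes | yes |
| Cystectomy itself | no | yes | no | no |
| Death | not listed | in tables only | in tables only | yes |
| Non-muscle-invasive relapse | no | not in text | not stated | not stated |

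No SAP column matches the first. SAP 3.11 differs by adding cystectomy and death. Table 61 has no cystectomy-only row, so its events may nearly coincide with the protocol composite. SAP 3.13 adds death and does not restrict the type of relapse.

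The second step is the size per affected patient, against the same composite with every relapse counted. N = 32 (SAP 3.1). Protocol 3.1 says "The study will be closed 2 years after the last patient inclusion", so apart from dropout there is almost no censoring before 24 months. SAP 3.12 does not say how an operated relapse is coded or censored, so the result depends on the convention.

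- **Kept at risk as event-free, no later event.** Without censoring, the Kaplan-Meier estimate is the event-free proportion, so one recoded patient adds 1/32 = 3.125 points. This was checked by simulation: N = 32, one patient with an event before month 9 recoded and followed past month 24, assumed 24-month event-free of 50%, 65% and 80%, and 1,500 draws per setting. With no dropouts the rise was 3.12 points at 12, 18 and 24 months in every draw. With two dropouts before month 24 it ranged from 3.12 to 3.42, and with four from 3.12 to 3.64.
- **Censored at relapse.** The factor (n − 1)/n drops out, so the estimate S becomes S × n/(n − 1). With an assumed 30 at risk the gain is S × (30/29 − 1) = S/29. For assumed 24-month S of 50%, 65% and 80% this is 1.7, 2.2 and 2.8 points.
- **Kept at risk, later event.** The event only moves. A relapse at month 7 replaced by a metastasis at month 15 (both assumed) gives +3.1 points at 12 months and 0 at 18 and 24.

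**The case against.** The strongest reply is that nothing is concealed. The SAP never calls EFS (specific) disease-free survival, and it states the surgery condition openly. Operated relapses are counted in 3.11, and 3.13 has no surgery exception. Muscle-invasive relapse and metastasis are also analysed separately in 3.15, 3.17, 3.18.1 and 3.18.4. This stands. A reader might infer that the sponsor replaced disease-free survival with a more favourable endpoint; the documents do not support that.

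A reader might also take the row missing from Table 66 as proof that operated relapses are dropped. It is not proof. The same table would result if those patients were recoded as plain bladder relapse, with cystectomy simply removed as an event type. The contrast between items 1 and 2 makes that less likely but does not exclude it. Similarly, Table 55 has a Yes row for cystectomy by 9 months that Tables 52 to 54 lack. This hints at one or more patients but gives no count.

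A large bias is another tempting inference. Assume independent 24-month risks of 20% for metastasis and 10% for death, relapse risk r of 10% to 30%, and a fraction f of 25% to 100% of relapses operated on. The gap is then 0.8 × 0.9 × r × f, from 1.8 to 21.6 points. The documents give none of these rates, and the top of the range needs every relapse to be operated on in a cohort enrolled as not having cystectomy. That range should carry no weight.

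Distortion of the Cox results is possible but unquantified. The same seven factors are modelled for 3.11, PFS and OS without the exception, so a discrepancy could be seen by comparison.

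**Conclusion.** The point holds in limited form and is minor. As worded, SAP 3.12 makes event status at relapse depend on later surgery, in a numbered secondary objective that the protocol does not contain. The protocol's surgery-independent composite has near equivalents in the SAP but no exact analysis.

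Per operated relapse with no later event, the upward shift is 3.1 to about 3.6 points or about 1.7 to 2.8 points, depending on an unstated coding rule and on the assumptions above. The total is unknown because the number of such patients is not given. For scale, the 95% half-width for a proportion of 65% at N = 32 is 1.96 × √(0.65 × 0.35/32) = 16.5 points. If operated relapses are in fact coded as plain bladder relapse, there is no shift and only the wording is wrong.

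The effect does not reach the primary endpoint, and no decision rule uses EFS (specific).

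**What to change.** - Add the protocol's disease-free survival to the SAP, under objective 1c (where Table 8 places the composite) or as its own section: time from treatment start to first muscle-invasive bladder recurrence or metastasis, each at its own date whatever surgery follows.
- State whether death is an event and, if so, that this departs from protocol 2.2. State how residual muscle-invasive disease at the response biopsy enters, since Table 49 has T2 and T4 rows and such patients were never disease-free.
- Keep EFS (specific), its tables and its Cox models only as a labelled post hoc supplementary analysis. State which relapses it counts (muscle-invasive only or any), whether death counts, and how operated relapses are coded, dated or censored.

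The cost is some rewording and a small re-run. Muscle-invasive relapse dates are in Table 83, and metastasis and death dates are already needed for 3.14, 3.17 and 3.18.4, so no new data are required. The disease-free survival estimate may be less favourable than EFS (specific).
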